8.5 Sample Size Re-estimation

The Residual Mean Square Error (RMSE) and the mean of the control group are two parameters used in determining the sample size goal ($N_{SSG}=78$) which are directly tied to the study cohort enrolled. The former value is directly proportional to the sample size and the latter applies its influence in defining the effect size. Thus the advertised statistical power of this trial may differ from the actual power if either differs from the initial values assumed. Consequently, the plan is to estimate both values using the accumulated data (internal interim estimate, IIE) when approximately half the subjects ($N_{SSG}/2$) have had their 1 year C-Peptide assessment. Since the initial values used are based on real data from four previous TrialNet studies, the re-estimation of each parameter will be a two-term weighted average using the number of subjects on which the IIE is based as the one weight (N_{IIE}) and the remaining number of subjects participants to be enrolled as the other weight ($N_{SSG}-N_{IIE}$). Algebraically, the re-estimate will be computed:

$$\hat{\sigma}_{Re-estimate}^2 = \frac{N_{IIE}\hat{\sigma}_{IIE}^2 + (N_{SSG} - N_{IIE})\hat{\sigma}_{Initial}^2}{N_{SSG}}$$

Similarly, re-estimation of the mean of the control group will be calculated. These new estimates will be used to calculate a new sample size goal for the trial.

It is important to note that this adaptive procedure is a non-comparative interim analysis (i.e., the observed treatment effect has no influence on the sample size re-estimation). Therefore, this analysis has no effect on the type I error. Note the re-estimation can be conducted by the analyst in a blinded fashion. The goal is to assure adequate statistical power at the completion

of the trial by assuring the two design parameters reflect accurately the study population being enrolled.

8.6 Interim Monitoring Plan

Interim analyses will be conducted periodically during the study and will be reviewed by the TrialNet DSMB for assessment of effectiveness and safety. The Lan-DeMets⁷⁴ spending function with an O'Brien-Fleming boundary will be used to protect the type I error probability from early and multiple testing and to assess the significance of the interim results that emerge during the trial⁸². The spending function that approximates the O'Brien-Fleming boundaries is:

$$\alpha_1(t^*) = 2 - 2\Phi\left[\frac{Z_{\alpha/2}}{\sqrt{t^*}}\right]$$

where t^* is the information fraction ($0 < t^* \leq 1$), α_1 is the α -level of the interim (one-sided) test and α is the type I error for one of the pair-wise tests (i.e., 0.025). The monitoring plan will allow for early termination based on the treatment effect on C-peptide values at 1 year of follow-up using the ANCOVA model described above.

The DSMB will also be informed if there is a serious lack of evidence of a treatment effect (i.e. futility analysis). The boundaries are based on the paper by Lachin⁸³. The study arm should be "closed" based on the futility of rejecting the null hypothesis at the completion of the trial if: $z_{ATG}(t^*) \leq 0.1$ when $0.5 \leq t^* < 0.75$ or if $z_{ATG}(t^*) \leq 1.0$ when $t^* \geq 0.75$ (z is the Wald test of the treatment effect coefficient). The same rule would be applied to the ATG/GCSF treatment group. These $t^* = 0.5$ and 0.75 are equivalent to when there are 39 and 59 participants with one-year C-peptide results, respectively. Lachin showed that a onetime use of either boundary for the design parameters above ($\theta \equiv Z_{1-\alpha} + Z_{1-\beta} = 3.00$) raises the type II error to approximately 0.15414 and 0.15611, respectively. For larger values of t^* the increase to the error probability is even less. Furthermore, by the laws of probability a single use of each rule will increase the type II error no more than the sum of the increase (i.e., $0.00414 + 0.00611 = 0.0103$).

[figure not shown]

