8.4 Sample Size and Power Calculations

The primary analysis will compare the difference in C-Peptide between experimental and placebo treatment groups at 12 months using $\log(Y_{Cp} + 1)$ transformation and ANCOVA model adjusting for gender, baseline age and the baseline value of $\log(Y_{Cp} + 1)$. Estimates of the mean and standard deviation of $\log(Y_{Cp} + 1)$ (expressed algebraically as: $\hat{\mu}_{\log(Y_{Cp} + 1)}$ and $\hat{\sigma}_{\log(Y_{Cp} + 1)}$) in the placebo group were derived from the last four TrialNet studies of early onset disease. The 90% confidence bound estimates were used to provide good confidence that this trial's study population characteristics fall within these limits to assure the advertised statistical power; the estimates are $\hat{\mu}_{\log(Y_{Cp} + 1)} = 0.360$ and $\hat{\sigma}_{\log(Y_{Cp} + 1)|X} = 0.167$ (i.e., the residual mean squared error regressing on gender, baseline age and C-peptide). The geometric-like mean of Y_{Cp} for the placebo group is $\exp(0.36) - 1 = 0.433$ nmol/L.

Using standard equations for the comparison of two means and a 1:1:1 allocation, a sample size of 78 participants (26 per group) with complete data would provide power of 85% to detect a 50% increase in the geometric-like mean in either experimental treatment group (compared to the control) using the Wald test (from the adjusted linear model) at the 0.025 level (one-sided). Thus the overall Type I error for both tests is approximately 0.05.

Assuming that 10% of the participants will have missing data (one-year MMTT was not done or subject withdrew prior to the one-year assessment), the sample size goal for this study will be set at 84 participants (28 per group).

The study will be closed to additional participants when the total number then randomized plus a fraction of those in screening (i.e., screening for eligibility) is expected to provide the proper number of eligible participants. Participants who had already conducted the initial screening visit at that time will be allowed to complete screening and be randomized if both consenting and eligible.

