10.3.6 Medical Monitor and Data Safety and Monitoring Board (DSMB)

All adverse events will be recorded on the adverse event forms, which will be sent to the local IRBs/REBs, per their reporting requirements, and to the Coordinating Center.

An independent physician will be designated to serve as the medical monitor for this study who will maintain regular contact with the study and the Study Chair. (S)he will review all adverse event reports, masked to treatment assignment, and will file event reports with regulatory authorities as appropriate.

The DSMB will meet approximately every 3 months and as needed to review indicators of safety. In addition, they will meet every 6 months to review the interim effectiveness and potential toxicity of the study treatments based on interim analyses of indicators of effectiveness and safety prepared by the TNCC separately by treatment group. The DSMB will independently evaluate whether there are grounds to modify or discontinue the study.

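### Section 8.6 defines the Lan-DeMets spending function as the level of each interim test, when it is the cumulative alpha spent; read literally, this slightly inflates the per-comparison type I error

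*Protocol*

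**What the plan says.** Section 8.6 adopts the Lan-DeMets approach with an O'Brien-Fleming boundary, with the stated purpose of protecting the type I error against early and repeated testing. Writing t for the information fraction, it prints α₁(t) = 2 − 2Φ(Z_{α/2}/√t). It sets α at 0.025, the type I error of one pairwise test, and says that α₁ "is the α -level of the interim (one-sided) test". It does not call α₁ cumulative.

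Section 8.4 sizes the trial with the Wald test "at the 0.025 level (one-sided") and adds: "Thus the overall Type I error for both tests is approximately 0.05".

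The number of efficacy looks is not fixed. Section 8.6 speaks of periodic interim analyses. Section 10.3.6 says of the DSMB that "they will meet every 6 months to review the interim effectiveness and potential toxicity" of the study treatments. The fractions 0.5 and 0.75 (39 and 59 participants) appear in section 8.6 only in the futility rule.

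**The concern.** α₁(t) is the total alpha spent from the start of the trial up to t. At the first look nothing has been spent before, so it is also the nominal level of that test. From the second look on the two differ. The nominal level must then be solved from the increment in α₁, given the correlation with the earlier statistics. A reader who takes the printed definition at its word would test every look at α₁(t), and the last at α₁(1) = 0.025, and would spend part of the alpha twice.

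With effectiveness reviewed every six months, a second look is to be expected. Crossing the boundary also has large consequences: under section 8.7 the placebo arm would normally close, and the second formal hypothesis could then no longer be tested. A threshold with that effect should have one meaning.

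**Working it through.** **Inputs from the protocol.** One-sided α = 0.025 per comparison (8.4, 8.6); control mean 0.360 on the log(Y+1) scale, residual SD 0.167, 26 per group, a 50% increase, 85% power (8.4). **Assumed:** the look schedules; equal arms with a shared control, so that the two comparisons correlate at 0.5.

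**1. The plan's own design figure.** The effect is log(1 + 1.5 × (e^0.360 − 1)) − 0.360 = 0.1408. The expected z is 0.1408 / (0.167 × √(2/26)) = 3.04. Power at one-sided 0.025 is Φ(3.04 − 1.96) = 0.860, consistent with the stated 85%.

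**2. The spending function.** Z_{α/2} = 2.2414 for α = 0.025.
- t = 0.5: 2 − 2Φ(2.2414/√0.5) = 0.00153
- t = 0.75: 2 − 2Φ(2.2414/√0.75) = 0.00965
- t = 1: 2 − 2Φ(2.2414) = 0.0250

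The function reaches exactly the total α at t = 1, as cumulative spending should.

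**3. Two readings, for looks at 0.5, 0.75 and 1.** Crossing probabilities come from recursive numerical integration of the Brownian-motion score under the null.

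| Look | Literal nominal level (z) | Literal cumulative error | Level from spending (z) | Cumulative error |
|---|---|---|---|---|
| 0.5 | 0.00153 (2.963) | 0.00153 | 0.00153 (2.963) | 0.00153 |
| 0.75 | 0.00965 (2.340) | 0.01012 | 0.00916 (2.359) | 0.00965 |
| 1 | 0.0250 (1.960) | 0.0279 | 0.0220 (2.014) | 0.0250 |

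The first look is identical; the readings part at the second.

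**4. Other schedules.** Family-wise error is from 1,000,000 simulated trials with two comparisons. For a single-look design it is 0.0454.

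| Looks | Per-comparison error, literal | Family-wise, literal | Correct final level (z) |
|---|---|---|---|
| 0.5, 1 | 0.0255 | 0.046 | 0.0245 (1.969) |
| 0.5, 0.75, 1 | 0.0279 | 0.051 | 0.0220 (2.014) |
| four equal | 0.0279 | 0.050 | 0.0220 (2.014) |
| five equal | 0.0288 | 0.052 | 0.0211 (2.031) |
| six equal | 0.0296 | 0.054 | 0.0204 (2.045) |

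With cumulative spending the per-comparison error is 0.0250 for every schedule, and the family-wise error is about 0.0455.

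**5. Variants.** If the interim boundaries are derived correctly but the final test is run at 0.025, the per-comparison error is 0.0255, 0.0277, 0.0283 and 0.0288 for two, three, five and six looks. If the futility rules were binding, the literal figures would fall to 0.0251, 0.0268, 0.0284 and 0.0290.

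**6. Power.** With a final z of 2.014, the final test alone has power Φ(3.04 − 2.014) = 0.847, against 0.860. Efficacy crossings at earlier looks can only add to 0.847, so, leaving futility stopping aside, the loss is at most about one percentage point.

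**The case against.** The strongest reply is that section 8.6 names a method that controls the error, states that control is its purpose, calls the expression a spending function and prints the right formula. α = 0.025 is correctly described as the type I error of a pairwise test, that is, the total to be spent. A statistician using standard Lan-DeMets software would hold 0.025 whatever the gloss on α₁ says. All of this stands, and it makes the inflation conditional on a literal reading.

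It is also fair to say that look-by-look boundaries and the final nominal level are commonly left to the SAP, which is not at hand. Their absence from the protocol is therefore no fault. The definition is different: the protocol chose to define the symbol, and the definition is wrong from the second look on.

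A reader might infer three stronger claims, and the protocol supports none of them.
- *The final test stays at 0.025, so the trial exceeds its stated error.* No section fixes the final critical value after interim looks. The 0.025 in section 8.4 is an input to the sample-size calculation.
- *The overall error of approximately 0.05 is lost.* Even on the literal reading, family-wise error is 0.046 to 0.054, close to that figure.
- *The inflation is larger, about 0.032 per comparison.* This needs looks at 0.5, 0.6, 0.7, 0.8, 0.9 and 1. At six-monthly reviews, a tenth of the information per review means 10 × 6 = 60 months of accrual, whereas section 1.1 expects two to three years. With even accrual over that time, six-monthly looks number about four (24/6) to six (36/6) and are equally spaced.

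**Conclusion.** The definition of α₁ in section 8.6 is wrong as written. Its practical effect is small and conditional. If each test, including the last, were run at α₁(t), the one-sided error per comparison would rise from 0.025 by about 0.0005 with one interim look at 0.5, by about 0.003 with looks at 0.5 and 0.75, and by about 0.004 to 0.005 with four or five equally spaced interim looks. The size depends on assumed schedules, since the only fractions named belong to the futility rule. A breach of type I error control is not shown. This is a minor correction, worth making because the wording permits two thresholds for a decision that could close the placebo arm.

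**What to change.** In section 8.6, define α₁(t) as the cumulative one-sided type I error spent by information fraction t for one pairwise comparison. Add that the critical value at each look after the first, including the final analysis, is obtained from the increment in α₁ since the previous look, given the earlier looks. An example would help: for looks at 0.5, 0.75 and 1, the nominal one-sided levels are 0.00153, 0.00916 and 0.0220, with a final z of about 2.01.

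In section 8.4, note that 0.025 is the total alpha per comparison and not the nominal level of the final test when interim efficacy looks have been taken.

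The cost is a few sentences and a slightly larger final critical value (1.97 to 2.05 for the schedules above, against 1.96). The power loss is very small, and standard software does the calculation.

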8.7 Interim Analysis Study Modification

Whether Lan-DeMets boundary is crossed or a futility decision rule indicates closure of an experimental arm, the course of action for the study is as follows. In case the futility decision rule indicates closure of one of the experimental arms (and the governing bodies concur), the trial should continue randomizing between the other remaining experimental treatment and placebo (1:1 ratio) since the corresponding hypothesis remains unaddressed. However, in the circumstance where the Lan-DeMets boundary is crossed the normal course of action would be to close the placebo arm. This would incapacitate the second formal hypothesis test thus leaving only the issue of which experimental treatment is "best" as the remaining question. However, it may or may not be reasonable to make this decision as well. To evaluate the evidence at the interim the plan is to use stochastic curtailment and compute the probability that the currently 'best' treatment (as defined by the decision rule above) is not the 'best' when the full sample size is reached. In the normal employment of stochastic curtailment in futility analysis the parameters used for the simulation are based on the alternative hypothesis. The

analogous parameters for this situation is to set the mean of the currently 'best' treatment to be lower than the other experimental treatment mean and determine the probability of a reversal. As with the normal application of stochastic curtailment, we will use the probability of 0.20 or less to stop accrual completely and invoke the decision rule for selecting the 'best' treatment immediately. Alternatively, the study would continue to its planned completion, randomizing between the two active treatment arms, until the projected probability of a re-ordering of the outcome (change in the selection of the superior treatment arm) is less than 0.2.

Our choice for setting the parameters for simulation is to set the 'best' treatment group at 25% lower than the other experimental treatment mean; these two parameters being centered at the midpoint between the two estimated experimental group means. This is consistent with the difference between the two treatment arms specified in the Simon selection at the completion of the trial (described above), should both arms be superior to the placebo.

The graph below provides an estimated probability of a 'best' selection reversal conditioned on the interim data (simulated under the condition of crossing the Lan-DeMets boundary and $t^* = 0.5$). The probability is primarily a function of the relative position of the 'lesser' mean to the positions of the placebo mean and the 'greater' mean (all means being estimates from the interim data). That is, the closer the 'lesser' mean is to the placebo, the less likely there could be a reversal in the selection of the 'best' treatment.

Additional analysis will assess potential adverse outcomes of treatment and will assess the incidence of all severe adverse events.

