1 INTRODUCTION

1.1 Study Overview

Title	ATG-GCSF in New Onset Type 1 Diabetes
IND Sponsor	National Institute of Diabetes and Digestive and Kidney Diseases (NIDDK)
Conducted By	Type 1 Diabetes Trial Network (TrialNet)
Protocol Chair	[name]
Accrual Objective	84
Study Design	Three-arm, 1:1:1 randomized, placebo controlled, double-blinded trial in which at least 28 subjects will receive active ATG-GCSF, at least 28 subjects will receive ATG alone and at least 28 subjects will receive placebo alone within 100 days from diagnosis of T1D. An adaptive design will be used to determine the variance of C-peptide over time and may require additional subjects to be enrolled in each group to preserve power.
Treatment Description	ATG will be administered at a dose of 2.5mg/kg as two divided IV infusions of 0.5mg/kg and 2mg/kg. GCSF will be administered at a dose of 6mg SC or if <44.5 kg a dose of 100 mcg/kg every two weeks for a total of 6 doses.
Study Duration	Enrollment is expected to occur over two-three years. Subjects will be followed up to 24 months from randomization in this protocol.
Objective	To determine the safety and ability of low dose ATG plus GCSF and low dose ATG alone to retain/enhance C-peptide production in new onset T1D patients demonstrating residual beta cell function.
Primary Outcome	The primary statistical hypothesis to be assessed in the study is whether the 2 hour area under the curve (change in baseline to 12 months) in residual beta cell function (C-peptide) will differ between those treated with ATG and GCSF or ATG alone as compared with placebo.
Secondary Goals	The study will also examine the effect of the proposed treatments on surrogate markers for immunologic and metabolic outcomes
Major Inclusion Criteria	Type 1 diabetes diagnosed within the past 100 days Age \geq 12 years < 46 At least one diabetes associated autoantibody

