In the situation where both hypotheses are rejected in favor of the experimental regimen, then it is appropriate to decide which experimental regimen should be considered first for additional clinical trials. If ATG and ATG+GCSF truly differ in efficacy, it is not expected that the difference would be as large as the effect size used in this design. Thus requiring the difference to reach statistical significance would be too stringent due to the lack of statistical power. The plan is to employ the method of Simon⁸¹ to select the treatment with the largest geometric-like mean in C-Peptide regardless of how small the difference is over the other experimental regimen. Formally, the decision rule is to select the experimental regimen with highest predicted mean based on the fitted linear regression model of C-Peptide used in the formal hypothesis tests. Given the one experimental treatment is associated with 25% higher mean (half of the design effect size) compared to the other experimental treatment, the probability is 96% that the most efficacious regimen will be selected with this decision rule. Even if the increase is only 12.5% (i.e., a fourth of the design effect size), the probability is 82% in making the right choice. Since under the null ($\mu_{Cp}^{ATG} = \mu_{Cp}^{ATG/GCSF}$) we consider selecting either treatment a non-error there is no contribution to the type I error, and therefore, no further adjustment is required to the α -level of the initial two pair-wise tests.

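### Section 8.7 gives up the second primary test once one arm crosses the efficacy boundary, although most or all of the placebo participants it needs are already randomised and due for follow-up

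*Protocol*

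**What the plan says.** Section 8.1 of the protocol sets two primary hypotheses: ATG plus GCSF against control, and ATG alone against control. Section 8.7 covers what happens at an interim analysis.

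- **Efficacy.** If the Lan-DeMets boundary is crossed, "the normal course of action would be to close the placebo arm". The stated consequence is: "This would incapacitate the second formal hypothesis test thus leaving only the issue of which experimental treatment is" best. The active arms are then compared by stochastic curtailment. Accrual stops if the projected probability of a reversed ordering is 0.20 or less; otherwise randomisation continues between the two active arms.
- **Futility.** If one experimental arm is closed for futility, the other continues against placebo, "since the corresponding hypothesis remains unaddressed".

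Section 8.4 introduces highest-mean selection for one setting only: "In the situation where both hypotheses are rejected in favor of the experimental regimen".

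On timing, section 1.1 says: "Enrollment is expected to occur over two-three years". Section 8.6 describes information fractions 0.5 and 0.75 as "equivalent to when there are 39 and 59 participants with one-year C-peptide results". Section 5.6 expects everyone randomised to complete all scheduled assessments whatever treatment they received, and section 1.1 follows participants to 24 months.

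**The concern.** Closing placebo to new entrants and losing the placebo comparison are different things. The second test is lost only if too few placebo participants have been randomised when the boundary is crossed, or if those randomised are not followed to month 12. The protocol's timing and follow-up rules point the other way on both counts.

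The section also treats like cases differently. Under futility, an open second hypothesis is the reason to continue. Under efficacy, the second hypothesis is equally open, yet it is dropped. At stake is one of two primary questions, given up to avoid a handful of placebo randomisations or none.

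**Working it through.** **1. The plan's own sample size.** Section 8.4 gives a placebo mean of 0.360 on the log(Y+1) scale, SD 0.167, a 50% increase and one-sided 0.025.
- Effect: log(1 + 1.5 × 0.4333) − 0.360 = 0.1408.
- n per arm = 2 × [(1.960 + 1.036) × 0.167 / 0.1408]² = 25.3, rounded up to 26. Power at 26 per arm is 86%.
- This agrees with the plan: "a sample size of 78 participants (26 per group) with complete data would provide power of 85% to detect a 50% increase".

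**2. How many are randomised at each look.** The target is 84, or 28 per group. The protocol gives no accrual curve, so I assume uniform accrual over T months with a proportion m (0 to 10%) missing the one-year result.

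Number randomised = min(84, results/(1 − m) + 12 × 84/T)

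| T (months) | At 39 results, m = 0 | At 39 results, m = 10% | Placebo still to randomise | At 59 results |
|---|---|---|---|---|
| 24 | 39 + 42 = 81 | 84 | 0-1 | 84 |
| 30 | 39 + 33.6 = 72.6 | 76.9 | 2-4 | 84 |
| 36 | 39 + 28 = 67 | 71.3 | 4-6 | 84 |

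So 80-100% are randomised at fraction 0.5 and 100% at 0.75. Crossing earlier is unlikely: at the design effect, a given arm crosses at a first look with probability 0.2% at fraction 0.25 and 2% at 0.33.

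**3. Boundaries.** The spending function in section 8.6 with α = 0.025 gives cumulative spend of 0.00153 at 0.5, 0.00965 at 0.75 and 0.025 at 1. With looks at those fractions the one-sided critical values are 2.963, 2.359 and 2.014.

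**4. How often one arm crosses alone.** I simulated 1,000,000 trials with three arms sharing one control, 26 evaluable per arm. With both arms at the design effect:
- Exactly one arm is across at the first crossing in about 48% of trials (about 23% at 0.5 and 25% at 0.75).
- In about 79% of those, the other arm exceeds 2.014 at full follow-up (90% after a crossing at 0.5, 69% after one at 0.75).
- If one arm has the design effect and the other has half of it on the log scale, the 79% becomes 34%. If the other has no effect, it becomes 3%.

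**5. Power of the second test on the randomised cohort.** This takes a crossing at 0.5 with accrual as in step 2 (m = 0), then 10% loss. Placebo evaluable: 22 × 0.9 = 19.8 to 27 × 0.9 = 24.3. Second active arm, which continues to 28: 28 × 0.9 = 25.2.

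Power = Φ(0.1408 / [0.167 × √(1/n₀ + 1/n₁)] − 2.014)
- 19.8 against 25.2: 78.6%
- 24.3 against 25.2: 82.9%

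At 1.96 these would be 80% and 84%. If active participants randomised after placebo closes are left out, so that controls are concurrent, 19.8 against 19.8 gives Φ(2.652 − 2.014) = 74% and 24.3 against 24.3 gives Φ(2.938 − 2.014) = 82%.

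**6. The selection rule after one rejection.** In the step 4 runs with both arms at the design effect, the second arm ends above the crossing arm without itself being significant in about 0.1% of one-arm crossings.

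**The case against.** The other side has five arguments.

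- **Closing may mean closing to accrual.** The actions in section 8.7 concern accrual and randomisation, and section 3.3 keeps participants masked until the end of the study. A reader might infer that placebo follow-up stops and the data are lost. The documents do not say so, and section 5.6 points the other way. This stands. What remains wrong is the statement that the test is incapacitated, with no provision to run it.
- **It is a considered choice.** The section states the trade-off openly and speaks of a normal course of action, and section 10.3.6 leaves the DSMB independent judgement. That is fair, but the reason given for the choice is factually wrong on the protocol's timing.
- **The size depends on assumptions.** The 79% is the favourable case. Fractions 0.5 and 0.75 come from the futility rule; efficacy looks are only described as periodic (section 8.6) or six-monthly (section 10.3.6). This stands.
- **Sample size re-estimation.** Section 8.5 may raise the target at about the half-way point. More placebo participants would then remain to be randomised, and the 80-100% would fall. This also stands.
- **The selection rule does little harm.** A reader might infer that the trial could readily recommend a regimen that never beat placebo. To be selected, the second arm must overtake an arm that has already crossed an O'Brien-Fleming boundary. Step 6 shows how seldom it does so without being significant itself. The mismatch with section 8.4 is one of consistency.

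**Conclusion.** The point holds in a limited form. Section 8.7 is wrong to say that closing placebo incapacitates the second primary test. At the looks where a crossing is realistic, 80-100% of the planned participants are already randomised, their follow-up is already required, and the second test would keep about 79-83% power against the planned 85%.

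With both arms at the design effect and looks at 0.5 and 0.75, the situation arises in about 48% of trials. The loss shrinks if the second arm is weaker, and nothing is lost if both arms cross at the same look. The figures rest on uniform accrual, the section 8.4 design values and no increase in sample size.

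This should be corrected, but it is not a defect that the trial's validity depends on. It does not support a claim that placebo data would be discarded, or that an unproven regimen is likely to be chosen.

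**What to change.** Amend section 8.7 to state that:

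1. Crossing the boundary stops only new randomisation to placebo.
2. Masked follow-up of everyone randomised continues to month 12 and beyond, as sections 1.1 and 5.6 already require.
3. The other hypothesis is still tested at its own Lan-DeMets boundary, using all randomised placebo participants. The text should also say whether active participants randomised after placebo closed enter that test.
4. Highest-mean selection applies when both nulls are rejected, as in section 8.4.

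The wording should be settled before any comparative interim result is seen. The cost is one protocol paragraph and matching DSMB wording, with no added participants. The downside is that final selection and unmasking wait for 12-month visits that are already scheduled.
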